#### 6.1.4.3 Evaluation of Best Overall Response

The best overall response is the best response recorded from the start of the treatment until disease progression/recurrence (taking as reference for progressive disease the smallest measurements recorded since the treatment started). The subjects best response assignment will depend on the achievement of both measurement and confirmation criteria.

Target Lesions	Non- Target Lesions	New Lesions	Overall Response	Best Response for this Category
-------------------	---------------------------	-------------	---------------------	---------------------------------------

				Also Requires:
CR	CR	No	CR	≥4 wks. confirmation
CR	Non- CR/Non- PD	No	PR	> 4 wks. confirmation
PR	Non-PD	No	PR	
SD	Non-PD	No	SD	documented at least once ≥4 wks. from baseline
PD	Any	Yes or No	PD	
Any	PD*	Yes or No	PD	no prior SD,
Any	Any	Yes	PD	PR or CR
* In exceptional circumstances, unequivocal progression in non-target lesions may be accepted as disease progression.				

Note: Subjects with a global deterioration of health status requiring discontinuation of treatment without objective evidence of disease progression at that time should be reported as "*symptomatic deterioration*". Every effort should be made to document the objective progression even after discontinuation of treatment.

Note: If subjects respond to treatment and are able to have their disease resected, the patient's response will be assessed prior to the surgery.

# 6.1.4.4 Evaluation of Bone Lesions:

Bone lesions will be evaluated either by CT or bone scan, whichever is deemed to be better suited by baseline studies. Since the size of the lesion is difficult to measure in a bone scan, particularly if it is not well visible in CT the following guideline will be used. Any ambiguity will require MRI for resolution:

- 6.1.4.4.1 Progression of bone lesions will be defined as follows:
  - Appearance of 1 or more new bone lesion in Bone scan, confirmed by a repeat bone scan in ≥6 weeks.
- **6.1.4.4.2** Response of bone lesions in bone scan will be defined by either a complete resolution (CR) at the metastatic sites or partial resolution (PR) of radiotracer uptake by a radiologist.

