## 6.0 Measurement of Effect

## 6.1 Antitumor Effect

For the primary endpoint, response and progression will be evaluated in this study using the new international criteria proposed by the Response Evaluation Criteria in Solid Tumors (RECIST) Committee [JNCI 92(3):205-216, 2000], which was also used by the two randomized trials of HD IL-2 being used as historic controls for this trial [35, 36]. The only change from RECIST v.1.1 being implemented in this study is a confirmation of new lesions or progressive disease (PD) by a second scan >6wks apart, based on the immune RECIST (irRC) criteria proposed by Wolchok. et. al that is appropriate for immune-related treatment response [91]. This is primarily because immune response often can take longer time as compared to chemotherapy before producing a radiographic response and during this time new lesions may arise which will eventually regress and if it were not for a second confirmation, these patients would be labeled to have failed therapy. In addition, the majority of mRCC responders to HD IL-2 usually produce a durable response (median response duration of 24 months), therefore, this change will not affect the outcome [35]. Additional criteria for bone lesions and clinical endpoints of pathologic fracture and cord compression are added to this study (see Section 6.1.4).

Changes in only the largest diameter (unidimensional measurement) of the tumor lesions are used in the RECIST v1.1 criteria outlined in http://www.recist.com/.

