## 6.1.3 Methods for Evaluation of Measurable Disease

All measurements will be done digitally on the PACs system. All baseline evaluations should be performed as closely as possible to the beginning of treatment and never more than 14 days before the beginning of the treatment.
The same method of assessment and the same technique should be used to characterize each identified and reported lesion at baseline and during follow-up using appropriate radiologic imaging.

Bone scans and CT scan of Chest, abdomen and pelvis with IV contrast will be performed at baseline. Since bone scan is not reliable for RCC, it will only be used to evaluate overall response when positive in baseline scan, and any new lesions found on bone scan must be verified with a CT.

Spiral CT and MRI. All CT scans will be Spiral CT and should be performed using a 5 mm contiguous reconstruction algorithm.

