#### 6.1.4.2 Evaluation of Non-Target Lesions

Complete Response (CR): Disappearance of all non-target lesions and normalization of tumor marker level.

Incomplete Response/Stable Disease (SD): Persistence of one or more non-target lesion(s) and/or maintenance of tumor marker level above the normal limits.

Progressive Disease (PD): Appearance of one or more new lesions and/or unequivocal progression of existing non-target lesions

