#### 11.2 Sample Size and Accrual

The previous studies show that the maximum RR for mRCC patients treated with HD IL-2 is 23% [35]. We expect a >60% improvement in this rate leading to a 36.8% RR for mRCC patients when treated with SABR and IL2. The calculation of the sample size is based on the RR and Simon's optimal two-stage design will be used with  $(\alpha,\beta)=(0.20, 0.20)$  [120]. The RR of 23% is set as the lowest desirable rate and 36.8% is the rate we are targeting. We chose type I error of 0.20 and type II error of 0.20. That is, if the true response rate is less than 23%, the probability of wrongly accepting the treatment for further study is 20%, and if the true response rate exceeds 36.8%, the probability of wrongly rejecting it for further study is 20%. According to the optimal two-stage design, a maximum of 33 patients will be needed. In the first stage, 17 patients will be evaluated. If 3 or fewer responses are observed, then the trial will be terminated for futility. Otherwise an additional 16 patients (second stage) will enter the trial. Finally, if more than 9 responses are observed among 33 patients, then the regimen

(SABR+IL-2) may be considered as the experimental arm of a Phase III trial. The average sample size for this phase II trial is 26.2 patients, and the probability of early termination is 0.43 for a drug with response probability of 23%.

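### Section 6.1.4.4.2 labels an unquantified fall in bone-scan uptake as PR, a category that non-target disease does not have, and the plan does not say which rule governs

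*Combined protocol and SAP*

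**What the plan says.** The bone rules belong to the section that governs the primary endpoint. Section 6.1 states: "Additional criteria for bone lesions and clinical endpoints of pathologic fracture and cord compression are added to this study". Section 6.1.5 defines the response rate as CR plus PR.

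- **Response of bone (6.1.4.4.2).** On bone scan, response is either complete resolution, labelled CR, or "partial resolution (PR) of radiotracer uptake by a radiologist". No percentage or lesion count is given.
- **Class of bone lesions (6.1.2).** Bone lesions are listed as non-measurable. Target lesions must be measurable, and everything else is non-target.
- **Non-target categories (6.1.4.2).** These are CR, incomplete response/SD, and PD. The middle category is "Persistence of one or more non-target lesion(s) and/or maintenance of tumor marker level above the normal limits".
- **Overall response (6.1.4.3).** An overall PR needs target PR with no non-target PD, or target CR with non-target Non-CR/Non-PD. There is no row for a patient without target lesions.
- **Standing of the test (6.1.3).** "Since bone scan is not reliable for RCC, it will only be used to evaluate overall response when positive in baseline scan".
- **Irradiated lesions (4.1.1, 6.1.2).** Section 4.1.1 requires an untreated site to be left so that response can be measured there. Section 6.1.2 bars treated lesions from serving as target lesions. It does not mention treated lesions that are non-target.
- **New bone lesions.** Section 6.1.3: "any new lesions found on bone scan must be verified with a CT". Section 6.1.4.4.1: "Appearance of 1 or more new bone lesion in Bone scan, confirmed by a repeat bone scan" at 6 weeks or more. Section 6.1.4.4 sends any ambiguity to MRI.

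**The concern.** One section creates a PR for a class of lesion that two neighbouring sections say can only be CR, incomplete response/SD or PD. The plan has no sentence ranking them. Because a PR counts fully toward the primary endpoint, a reader scoring patients needs to know whether a bone-scan PR can make a responder.

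The question matters most where nothing else can produce a PR, namely in a patient with no target lesion. There the result would rest on a judgement without a threshold, from a test whose reliability in this disease the protocol itself doubts. If the bone site had been irradiated, fading uptake could reflect the local effect of SABR, whereas the stated aim is to measure response away from treated sites.

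A second, smaller gap concerns progression. The two sections name different confirmations for a new bone-scan lesion, and this bears on PFS, time to progression and response duration.

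**Working it through.** **1. Tracing a partial fall in bone-scan uptake through the rules**

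| Patient | Under 6.1.4.4.2 | Under 6.1.2, 6.1.4.2 and 6.1.4.3 |
|---|---|---|
| Target lesions PR, bone partly faded | bone PR | overall PR (from the targets) |
| Target lesions CR, bone partly faded | bone PR | overall PR (target CR, non-target Non-CR/Non-PD) |
| Target lesions SD, bone partly faded | bone PR | overall SD |
| No target lesion, bone partly faded | bone PR | no row in the table |

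In the first two rows the sections agree on the overall result. In the third, the table settles the matter if it is applied strictly. In the fourth, 6.1.4.4.2 is the only rule that offers a PR.

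**2. Can the fourth patient enrol?** Section 3.1.3 asks for more than one lesion and a combined diameter above 1.5 cm. It does not ask for measurable disease in the sense of 6.1.2. A patient whose lesions are all in bone can satisfy it.

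**3. Irradiated bone.** Section 4.1.3.1 allows bone lesions to be irradiated. The exclusion in 6.1.2 is worded for target lesions, and bone is never a target lesion, so the exclusion does not reach it. Section 6.1.4.5 makes an exception for treated sites in the case of fracture; 6.1.4.4.2 makes none for response. Irradiated bone is thus left in by omission, not by express statement.

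**4. The decision rule, reproduced.** Inputs from 11.2: "We chose type I error of 0.20 and type II error of 0.20"; "The RR of 23% is set as the lowest desirable rate and 36.8% is the rate we are targeting". Stage 1 has 17 patients and stops at 3 or fewer responses. Stage 2 adds 16, and more than 9 responses in 33 is a positive result. With X1 ~ Bin(17, p) and X2 ~ Bin(16, p):

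- P(stop at stage 1) = P(X1 ≤ 3)
- Expected N = 17 + 16 × [1 − P(stop)]
- P(go) = sum over x = 4 to 17 of P(X1 = x) × P(X2 ≥ 10 − x)

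At p = 0.23, P(stop) = 0.427 (stated 0.43), expected N = 17 + 16 × 0.573 = 26.2 (stated 26.2), and P(go) = 0.197, within the 0.20 limit. At p = 0.368, P(go) = 0.805, which meets 80% power. A search over designs with maximum N from 20 to 41 returns the same 3/17, 9/33 design. The design is correct as stated, and no figure in 11.2 is in dispute.

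**5. Sensitivity of the rule.** One patient in 33 is 1/33 = 3.0 percentage points. The documents give no frequency of bone-scan-only PRs, so the increments below are assumptions applied to a true response rate of 23%.

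| Apparent response rate | P(stop at stage 1) | P(go) |
|---|---|---|
| 23% (no inflation) | 0.427 | 0.197 |
| 25% | 0.353 | 0.281 |
| 26% | 0.319 | 0.327 |
| 28% | 0.256 | 0.424 |
| 29% | 0.228 | 0.474 |

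An average of one extra responder per 33 corresponds to about 26%, and two to about 29%.

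**6. Progression.** Section 6.1.3 requires CT verification of a new bone-scan lesion, and 6.1.4.4.1 a repeat bone scan. Neither mentions the other's condition. They can be applied together, but the plan does not say that they must be.

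**The case against.** The strongest reply is that 6.1.4.4.2 describes how bone lesions respond and does not assign the patient's overall response, which is the table's task. On that reading partly faded bone is Non-CR/Non-PD, and a patient with stable target lesions is SD. This stands, and it is why a broader reading fails: a reader might infer that any patient with stable target lesions and fading bone uptake becomes a responder, but the table does not support that. It leaves the patient without target lesions, for whom the table gives no answer.

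Other parts of the reply also stand:

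- Restricting bone scan to patients positive at baseline limits its use and does not itself conflict with 6.1.4.4.2. CT may replace bone scan where better suited, and MRI resolves ambiguity. Neither supplies a PR threshold.
- The lack of a confirmation scan is not peculiar to bone, since an ordinary target-lesion PR has none either.
- A reader might infer that the plan counts irradiated bone as response. No text says so, and 4.1.1 points the other way. The gap is one of omission.
- A reader might infer that a persistent new focus without a CT correlate is PD in one section and not in the other. The two conditions can be cumulative, and MRI is available for such a case.
- The inflation figures have no source in the documents. That one responder can tip a 9-versus-10 boundary is true of any misclassification.

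**Conclusion.** The point holds in a limited form. The PR label in 6.1.4.4.2 has no threshold and no counterpart among the non-target categories, and no text ranks the rules. The practical exposure is mainly patients without target lesions, together with irradiated bone that is not expressly excluded. The new-lesion confirmation needs a reconciling sentence; it is not an outright contradiction.

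The size of the effect on the response rate cannot be derived from the documents, which give neither the share of patients without target lesions nor the frequency of bone-scan-only PRs. The rise in P(go) from 0.197 to 0.327 or 0.474 shows how sensitive the rule would be to an assumed 3- or 6-point inflation, and does not forecast one. The issue is worth closing before responses are scored, because it concerns the primary endpoint and can be settled with categories already in the plan.

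**What to change.** In 6.1.4.4.2, state that bone lesions followed by bone scan are non-target; that a partial reduction in uptake is entered as Non-CR/Non-PD in the 6.1.4.3 table and is not by itself an overall PR; and that SABR-treated bone sites are not used for response.

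In 6.1.4.4.1, state that a new bone-scan lesion needs both the repeat scan at 6 weeks or more and the CT verification already required by 6.1.3, with MRI for ambiguity as now written.

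**Cost.** The sample size and decision rule do not change (17 + 16 = 33). A genuine partial response confined to bone will no longer count toward the response rate. A few patients may need an additional CT: 5.2.7 and 5.3 make CT conditional on soft-tissue metastasis, and only the table in 5.4 lists it without condition. That CT is not a new requirement, since 6.1.3 already calls for it.

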# 6.1.4.5 Evaluation of Pathologic Fracture:

Any clinical suspicion of pathologic fracture will prompt radiologic evaluation with plain film, CT or MRI as appropriate and if confirmed by a radiologist, will constitute progression, unless it is at a treated site, in which case a treatment-related toxicity will be considered.

# 6.1.4.6 Evaluation of spinal cord Compression or Cauda equina compression:

Any clinical suspicion of cord or cauda equine compression will prompt radiologic evaluation with MRI (CT myelography if patient is not eligible for MRI) as appropriate and if confirmed by a radiologist, will constitute progression.

#### 6.1.5 Response Rate and clinical response:

Response rate (RR) is defined by combining CR and PR. Clinical response is defined by combining CR, PR, and SD.

#### 6.1.6 Duration of Response

Duration of overall response: The duration of overall response is measured from the time measurement criteria are met for CR or PR (whichever is first recorded) until the first date that recurrent or progressive disease is objectively documented (taking as reference for progressive disease the smallest measurements recorded since the treatment started).

The duration of overall CR is measured from the time measurement criteria are first met for CR until the first date that recurrent disease is objectively documented.

Duration of stable disease: Stable disease is measured from the start of the study registration until the criteria for progression are met, taking as reference the smallest measurements recorded since the treatment started.

#### 6.1.7 Progression-Free Survival

Progression-free survival (PFS) is defined as the duration of time from the date of registration to time of progression or date of death due to any cause.

#### 6.2 Safety/tolerability

Analyses will be performed for all subjects having received at least one fraction of SABR and one cycle of HD IL-2. The study will use the CTCAE version 4.0 for reporting of non-hematologic adverse events (http://ctep.cancer.gov/reporting/ctc.html) and modified criteria for hematologic adverse events (Appendix #/letter).

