## 4.2.1 Treatment Dosage and Administration

HD IL-2 will be administered at a dose of 600,000 IU/kg every 8h for a total of up to 14 doses (considered as one cycle), followed by a one week break and then another cycle of the same dose over another week. Each HD IL2 course consists of two cycles of up to 14 doses each separated by a week of rest. A total of three courses may be administered for patients without progression at the discretion of the medical oncologist. Patients will be admitted to the ICU of the corresponding hospital for IL-2 treatment and close monitoring according to the HD IL-2 algorithm (appendix B). Patients will undergo placement of a central venous catheter, typically a PICC line, before each course of therapy.

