## 4.2.1.1 Toxicities and Dosing Delays/Dose Modifications

Any subject who receives treatment on this protocol will be evaluable for toxicity. Each patient will be assessed for the development of toxicity according to the Time and Events table (5.4). Toxicity will be assessed according to the NCI Common Toxicity Criteria for Adverse Events (CTCAE), version 4.0. Dose adjustments should be made according to the system showing the greatest degree of toxicity.

Treatment with HD IL-2 will be modified by withholding doses of IL-2 rather than continuing therapy at a reduced dose, according to the current guidelines followed at UTSW. Doses of IL-2 will be withheld for multiple indications as listed in the table below including hypotension refractory to fluids and pressors, anuria for more than 24 hours and unresponsive to fluid replacement and low-dose dopamine, respiratory distress requiring more than 4 L of oxygen to maintain O2 saturation greater than 95%, confusion, sustained ventricular tachycardia or any sign or symptom of myocardial ischemia or myocarditis, metabolic acidosis with HCO3 less than 18 despite attempts to correct with IV HCO3; atrial fibrillation, documented systemic infection, or any other serious toxicity that is not controlled at time of next dose.

The following table published by Schwartzentruber [102] and included in the standard HD IL-2 administration guidelines of UTSW as described in Appendix B summarizes the guidelines that will be followed for discontinuation of HD IL-2:

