#### 5.1.18 Pulmonary Function Tests

#### 5.1.19 Cardiac Stress Test

## 5.2 Procedures During Treatment

SABR treatment requires one week for planning and one week for delivery of the 1 or 3 fractionation schemes. HD IL-2 must begin within 84 hours of the last SABR fraction. Each course of HD IL-2 consists of two cycles of approximately two weeks each (12-14 IV infusions q8h followed by about 9 days of break) requiring a total of four weeks.

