## 5.5 Removal of Subjects from Study

Subjects can be taken off the study treatment and/or study at any time at their own request, or they may be withdrawn at the discretion of the investigator for safety, behavioral or administrative reasons. The reason(s) for discontinuation will be documented and may include:

- 5.5.1 Subject voluntarily withdraws from treatment (follow-up permitted);
- 5.5.2 Subject withdraws consent (termination of treatment and follow-up);

5.5.3 Subject is unable to comply with protocol requirements; patients must be withdrawn from the trial and replaced if they failed to receive at least one cycle of HD IL-2

- 5.5.4 Subject demonstrates disease progression (unless continued treatment with HD IL-2 is deemed appropriate at the discretion of the medical oncologist);
- 5.5.5 Subject experiences toxicity that makes continuation in the protocol unsafe;
- 5.5.6 Treating physician judges continuation on the study would not be in the subject's best interest;
- 5.5.7 Subject becomes pregnant (pregnancy to be reported along same timelines as a serious adverse event);
- 5.5.8 Development of second malignancy (except for basal cell carcinoma or squamous cell carcinoma of the skin) that requires treatment, which would interfere with this study;
- 5.5.9 Lost to follow-up.

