#### 6.1.1 Definitions

Evaluable for toxicity. All subjects will be evaluable for toxicity from the time of their registration.

Evaluable for objective response. Only those subjects who have undergone SABR and one course of HD IL-2, and have had their disease re-evaluated at least at two occasions (8wk and 16wk) will be considered evaluable for response. These subjects will have their response classified according to the definitions stated below.

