#### 7.5 Stopping Rules

The study will be stopped if the combination treatment of SABR and HD IL-2 in the interim annual analysis is determined to confer significantly increased Grade 3-5 toxicity as reported in the literature from the treatments performed alone.

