# 11.3 Data Analyses Plans

This is a single-arm Phase II trial of SABR and HD IL-2 for mRCC patients. PFS and OS, will be estimated using the Kaplan-Meier approach along with the 95% confidence interval. Exact binomial method will be used to calculate the response rate, toxicity and the corresponding 95% confidence interval. One-sample log-rank test [121] will be used to test if the survival endpoints such as OS or PFS are significantly different from those in the historical control reported in McDermott et. al [35].

Generalized estimating equation (GEE) analysis will be conducted to test if the median number of spots in Elispot of the PBMC collected from patients are significantly different over time (before starting of treatment and after SBRT, at 8 weeks and six months). T-Cell proliferation SI will also be evaluated in the same manner.

HRQol, CEA and quality adjusted survival time analysis is described in Section 10.

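### Section 6.2 limits the safety analysis to patients who had SABR and one HD IL-2 cycle, contradicting 4.2.1.1 and 6.1.1, so SABR-treated patients who never get a cycle fall outside the analysed toxicity rate

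*Combined protocol and SAP*

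**What the plan says.** Three sections of the combined protocol and SAP describe the toxicity population.

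- Section 6.2, Safety/tolerability: "Analyses will be performed for all subjects having received at least one fraction of SABR and one cycle of HD IL-2". This is the only place that says who enters the safety analysis.
- Section 4.2.1.1: "Any subject who receives treatment on this protocol will be evaluable for toxicity".
- Section 6.1.1: "All subjects will be evaluable for toxicity from the time of their registration".

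Other sections bear on who falls between them.

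- Section 4.1.3 places radiation in the week before the first HD IL-2 cycle.
- Section 5.5.3 says that "patients must be withdrawn from the trial and replaced if they failed to receive at least one cycle of HD IL-2".
- Section 4.2.1 describes HD IL-2 as given "for a total of up to 14 doses (considered as one cycle"), with no minimum. Section 5.2 describes a cycle as "12-14 IV infusions q8h followed by about 9 days of break".

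The sections that use the rate do not settle the matter. Section 11.3 says "Exact binomial method will be used to calculate the response rate, toxicity and the corresponding 95% confidence interval" without naming a denominator. The Stopping Rules section (numbered 7.5 in the text, after the adverse event reporting requirements) stops the study if the annual interim analysis finds that the combination confers "significantly increased Grade 3-5 toxicity as reported in the literature from the treatments performed alone". It does not say which patients are counted.

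Collection of events is wider than the analysis. Section 4.5 keeps subjects removed from therapy in follow-up, and 7.3 monitors every subject with an adverse event. Sections 7.5.2 and 7.6.1 send all serious events to the DSMC, which under 12.5 also reviews adverse events quarterly.

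**The concern.** Tolerability and toxicity form a stated secondary objective (2.2.7). The reported rate should not depend on which section the analyst follows, but here it does.

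The narrowest definition is also conditional on something that happens after treatment has started. To enter the 6.2 set, a patient already exposed to SABR must go on to receive an HD IL-2 cycle. The reason for not going on may be an adverse event. A rate computed only in those who continued then describes patients selected partly on the outcome being measured. Section 5.5.3 reinforces this, because the patient is replaced as well as omitted, and nothing says that replacement leaves the safety analysis untouched.

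**Working it through.** **Step 1. Compare the definitions, patient by patient.**

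| Patient | 4.2.1.1 | 6.1.1 | 6.2 |
|---|---|---|---|
| Registered, no treatment | out | in | out |
| SABR, no HD IL-2 | in | in | out |
| SABR, first HD IL-2 cycle cut short | in | in | depends on what one cycle means |
| SABR and a full HD IL-2 cycle | in | in | in |

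The second row is the defect, and it needs no interpretation. The first row is a lesser mismatch between 4.2.1.1 and 6.1.1. The third depends on whether 4.2.1 (no minimum) or 5.2 (12 to 14 infusions) defines a cycle.

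**Step 2. The plan's own figures.** The plan states no toxicity rate and no size for the safety set. The nearest checkable figure is the two-stage design in 11.2: stop at 3 or fewer responses in 17, succeed at more than 9 in 33, with response rates of 23% and 36.8%. Exact binomial calculation gives:

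- probability of early termination at 23%: 0.427 (stated 0.43);
- average sample size: 17 + (1 − 0.427) × 16 = 26.2 (stated 26.2);
- type I error 0.197 and power 0.805 (targets 0.20 and 0.80).

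The design reproduces, so 33 is a sound planning number for response. It is not a stated size for the 6.2 set, and the Study Summary gives a maximum of 38. Using 33 below is an assumption.

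**Step 3. How far the rate can move.** Let x of the 33 in the 6.2 set have an event, so p = x/33. Let m treated patients lie outside it, k of them with an event.

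- 6.2 rate: x/33
- any-treatment rate: (x + k)/(33 + m)
- change: (k − pm)/(33 + m)

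The change runs from −pm/(33 + m) when k = 0 to +(1 − p)m/(33 + m) when k = m. Its size is therefore at most m/(33 + m), reached only if p is 0 or 1. It is upward when k/m exceeds p and downward when k/m is below p. The value of m is assumed.

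| m | Bound, set of 33 | Bound, set of 38 |
|---|---|---|
| 1 | 1/34 = 2.9 points | 1/39 = 2.6 points |
| 2 | 2/35 = 5.7 points | 2/40 = 5.0 points |
| 3 | 3/36 = 8.3 points | 3/41 = 7.3 points |

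**Step 4. An illustration away from the extremes.** Assume 10 of 33 with a Grade 3-5 event: 30.3%, exact 95% interval 15.6% to 48.7%.

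- m = 1: any-treatment rate from 10/34 = 29.4% to 11/34 = 32.4%, a change of −0.9 to +2.0 points.
- m = 3: from 10/36 = 27.8% to 13/36 = 36.1%, a change of −2.5 to +5.8 points.

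The 6.2 rate stays at 30.3% whatever happened to the omitted patients.

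**The case against.** The best defence is that the objective concerns the combined regimen. A rate in patients who received both modalities answers that question directly. This stands, and it is why that rate should be kept alongside the wider one. It does not explain why two other sections call the omitted patients evaluable.

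The defence is stronger for the stopping rule, which compares the combination with each treatment alone. A reader might infer that an any-treatment set should simply replace whatever the rule uses. The documents do not support that: a SABR-only patient has not received the combination. Section 1.3 describes HD IL-2 toxicity as significant, affecting multiple organ systems and requiring ICU admission, while 1.2 and 1.4 call the safety of SABR excellent. On those descriptions, SABR-only patients could dilute the monitored rate.

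A reader might also infer that events in the omitted patients are lost. They are not: they fall outside one analysed rate, but collection, DSMC reporting and quarterly review continue.

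A third tempting reading is that patients stopped during cycle 1 are certainly excluded. Section 4.2.1 sets no minimum number of doses, and 5.2 is a scheduling description, so that exclusion is possible but not established.

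Finally, the effect may be small against the sampling error of a single-arm trial of this size. That is fair, and the illustration above shows it. It limits the size of the point but does not remove the contradiction.

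**Conclusion.** The point holds and should be fixed. Section 6.2 as written contradicts 4.2.1.1 and 6.1.1, and following it drops patients exposed to SABR because of an event after exposure. Confidence is high on the wording and on who is omitted. It does not extend to the effect.

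The number affected is unknown and so is the direction. A reader might infer that 6.2 makes the regimen look safer than it is. That follows only if toxicity is more frequent among the omitted patients than in the 6.2 set, and nothing in the documents shows this. The size is bounded by m/(33 + m), on two assumptions: the value of m, and a 6.2 set of 33 when the Study Summary allows up to 38 subjects.

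**What to change.** 1. In 6.2, define the safety set for the toxicity analysis in 11.3 as all subjects who received any protocol treatment: one or more SABR fractions, or any HD IL-2 dose. Name it in 11.3.
2. Align 4.2.1.1 and 6.1.1 with that set. This narrows 6.1.1, so state that events in registered, untreated subjects are listed separately.
3. Report the rate in subjects who received both modalities next to the any-treatment rate.
4. In the stopping rule, state which set the comparison uses. Because it concerns the combination, show the both-modalities rate together with the any-treatment rate, not the any-treatment rate alone.
5. In 5.5.3, state that replacement affects only the response-evaluable count and does not take a treated patient out of the safety set. Reconcile its withdrawal from the trial with the continued follow-up in 4.5.
6. Reconcile 4.2.1 and 5.2 on what counts as one cycle when defining the both-modalities set.

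The cost is protocol wording and one extra toxicity table. The data are already collected, provided 4.5 is confirmed as governing follow-up of replaced patients. The reported rate may rise or fall.
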